### 2.1.4. Interim Analysis

Not applicable

### 2.1.5. Data Listings

Patients' data listings will be selected data supportive of summary statistical tables, including derived/calculated data from statistical process. These key data listings will be performed on selected analysis sets according to the focus of the listings and will be sorted as appropriate.

## 2.2. Sample size calculation

The primary endpoint of the study is to demonstrate a significantly greater improvement from baseline in Regurgitant Volume (assessed by echo CoreLab) associated with the CMCS at 12 months, relative to the Control group.

### Parameter of Interest

The parameter of interest for each treatment group is the mean change from baseline in regurgitant volume, in milliliters, at 12 months.

### Hypotheses

H0:  $\mu_{\text{CARILLON}} = \mu_{\text{CTL}}$ ;

Ha:  $\mu_{\text{CARILLON}} \neq \mu_{\text{CTL}}$ ;

where  $\mu_{\text{CARILLON}}$  is the mean change in regurgitant volume for those randomized to the Treatment group, and  $\mu_{\text{CTL}}$  is the mean change in regurgitant volume for those randomized to the Control group.

### Sample Size Estimation

Sample size is calculated using a comparison of means (Student's t test). The minimum required sample size was calculated under the following assumptions:

## STATISTICAL ANALYSIS PLAN

REDUCE\_FMR - SAP\_V2  
2018\_08\_06\_CT

REDUCE FMR Trial

Page 14/22

- Significance level two-sided 0.05;
- Statistical power to detect design alternative hypothesis is 80%;
- Hypothesized mean regurgitant volume change (baseline to 12-month): Control group = -2.4ml; Treatment group = -12.4ml;
- Hypothesized standard deviation: Control group = 13ml; Treatment group = 13ml;
- 3:1 randomization allocation.

Under the assumptions outlined above, the estimated minimum required sample size is 76 subjects (57 Treatment, 19 Control).

A total of 120 subjects at up to 20 centers will be randomized, allowing for approximately 30% attrition (mortality, missing data and loss to follow-up) in the first 12 months of follow-up.

### 2.3. Analysis Sets

#### 2.3.1. Databases

Core laboratory Excel databases will be used to analyze hemodynamic and echocardiographic assessments.

The CEC will be responsible for adjudicating complications reported during the study that are related to study endpoints (objectives), the procedure or the device. The CEC AE review Excel database will be used to analyze safety endpoints (MAE and HF-hospitalizations).

All other analysis will be done on the e-CRF clinical database.

#### 2.3.2. Definition of patient populations

5 populations will be defined:

- The enrolled population will include all patients who consented to participate to the study.
- The screen failure population will include all enrolled patients who did not meet all eligibility criteria or randomized to treatment group but procedure discontinued before an implant attempt. Only a listing of these patients will be presented.
- The Intent-to-Treat (ITT) population will include all patients who fulfill all eligibility criteria and either underwent the procedure and on whom a device implant was attempted, or are considered as control patients.

This population will therefore include all randomized patients except the patients for whom the procedure was discontinued before an implant attempt (see Fig 1 below).

This population will be analyzed regardless of the treatment actually received: if there is an error in treatment (i.e. subject was not treated as randomized), the analysis will be performed according to the randomized group assignment, not the treatment actually received.

- The As -Treated (AT) population will include all ITT patients who left clinic with the randomized therapy administered (i.e., randomized to Treatment group and received a permanent implant, or randomized to Control group)

This population will therefore include all randomized patients except the patients who underwent the procedure but were not implanted (see Fig 1 below).

This population will be analyzed according to the treatment actually received: if there is an error in treatment (i.e. subject was not treated as randomized), the analysis will be performed according to the treatment actually received, not the randomized group assignment.

- The Per Protocol (PP) population will include all AT patients who received randomized therapy, assessors remained blinded, and who did not receive alternative or confounding therapies (e.g., CRT therapy, transplant, stenting, etc.) through the primary endpoint timeframe of the study, who did not met any major deviation (see 2.3.3).

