4.2.2.1 Echocardiographic Assessments

The site echosonographer will conduct intra-procedure echocardiographic assessments and cannot be blinded to the subject's treatment assignment. In order to ensure that

study subjects remain blinded during scheduled follow-up echocardiograms, sonographers at each participating site will be instructed on preserving blinding prior to study start. Specific blinding procedures which will be followed by site sonographers, include:

- Keeping the echo screen faced away from the subject during the procedure
- Not discussing any details of the echo results with a study subject
- Not discussing the treatment assignment of a study subject, especially with the blinded study personnel or any non-study hospital staff

All baseline and follow-up echocardiographic analysis will be performed by an independent echocardiography corelab. A designated member of the corelab staff will remove all subject identifying information (including the date and visit interval) and digitally mask the coronary sinus/great cardiac vein (location of device). This will be done for all views required to assess the echocardiographic endpoints related to mitral regurgitation and left ventricular hemodynamics. This will ensure that the designated corelab assessor will always remain blinded.

For those parameters that are unavoidably affected by digital masking (e.g., mitral annular dimensions), an unblinded assessor will be used to gather the most accurate information without hindrance of the digital masking.

Echocardiographic analysis will be done in batches, with multiple subjects (Treatment and Control) at different visit intervals analyzed within the same batch, at the same time, for both consistency and blinding purposes. (Reference Appendix E: Echocardiogram Protocol.)

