6.2 Study Analyses

The primary analyses will be conducted according to the principles of intent-to-treat. All subjects will be analyzed according to randomized group assignment, and subjects randomized to the Treatment group but who do not receive a permanent implant will be included. If any subject does not have endpoint data available (12-month data), the primary analysis will assume that data as missing and that subject's data will not be included in the primary analysis.

In addition, a series of supportive, sensitivity analyses will be performed to assess the robustness of the primary analysis results, including imputing the last value observed (last value carried forward) for all missing endpoint evaluations.

Additional subgroup analyses will be conducted for all primary and secondary endpoints on as-treated and per-protocol cohorts defined as:

- **As-treated:** All subjects who left clinic with the randomized therapy administered (i.e., randomized to Treatment group and received a permanent implant, or randomized to Control group)
- **Per-protocol:** All subjects who received randomized therapy, assessors remained blinded, and who did not receive alternative or confounding therapies (e.g., CRT therapy, transplant, stenting, etc.) through the primary endpoint timeframe of the study

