### 2.3.3. Protocol Deviations

On a case-by-case basis, all protocol deviations will be reviewed and will be classified as “minor” or “major” according to the possible impact expected on primary results.

Patients meeting at least one of the following major deviations may be excluded from the PP population:

- At least one eligibility criterion not fulfilled;
- Treatment different from the randomized group assignment;
- Unblinded assessor(s);
- Unblinded subject(s);
- Patient who received alternative or confounding therapies (e.g., CRT, transplant, stenting, etc.);
- Study Windows not respected

All protocol deviations other than those defined in this section will be considered as minor and will not lead to patient exclusion from the PP population.

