### 2.4.2. **Primary Endpoint**

The primary analysis will be performed on the Intent to treat (ITT) population.

The primary efficacy endpoint is to compare the change in regurgitant volume from baseline at 12 months between the treatment and control groups using a two-sided, two-sample t-test (or Wilcoxon Rank sum test as appropriate). The corresponding 95% confidence interval on the between-group difference will also be calculated and presented.

A sensitivity analysis of the primary efficacy endpoint analysis on the ITT population will be performed, using the last observation carried forward (LOCF) missing data imputation on the regurgitant volume at 12 months. The same comparison analysis as mentioned above for the primary efficacy endpoint will be performed.

Two other additional analyses will be performed on the primary efficacy endpoint on:

- As-treated population
- Per-protocol population

The same comparison analysis as for the primary efficacy endpoint mentioned above will be used

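### SAP 2.3.2 gives conflicting rules on whether a randomized patient found to be ineligible belongs to the ITT set used for the primary analysis

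*SAP*

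**What the plan says.** SAP 2.4.2 (Primary Endpoint) fixes the set: "The primary analysis will be performed on the Intent to treat (ITT) population". Two statements in SAP 2.3.2 make eligibility a condition of being in it:

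- The first ITT sentence: the set "will include all patients who fulfill all eligibility criteria and either underwent the procedure" and had an implant attempt, or is a control patient. Grammatically the eligibility condition governs both arms.
- The screen failure bullet: that set holds "all enrolled patients who did not meet all eligibility criteria or randomized to treatment group but procedure discontinued before an implant attempt", and "Only a listing of these patients will be presented". SAP 2.3.2 defines enrolled as everyone who consented, so this wording is not limited to patients who were never randomized.

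Four statements point the other way:

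- The very next ITT sentence in SAP 2.3.2: "This population will therefore include all randomized patients except the patients for whom the procedure was discontinued before an implant attempt". It names one exception, which is not ineligibility.
- SAP 2.3.3 lists "At least one eligibility criterion not fulfilled" among the major deviations. The only consequence it attaches is possible exclusion from the per-protocol set.
- SAP 2.4.1.2 tabulates major deviations on the ITT population, by category.
- Protocol 6.2: "All subjects will be analyzed according to randomized group assignment", with no eligibility condition.

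SAP 2.3.2 also says that the sponsor reviews and approves the assignment of patients to populations before the database is locked.

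**The concern.** An ITT set should be fixed by randomization. If membership also depends on eligibility, it depends on a judgement that can be revisited after allocation. Here one section supports both answers, so whoever assigns populations could keep or remove the same patient and cite the SAP either way.

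The timing matters. Assignment is approved before lock, but 12-month outcomes may already exist by then. Protocol 4.3 allows a subject to be unblinded after that subject's own 12-month visit, and SAP 1.3.5 allows unblinding once all 12-month visits are complete. No text supplied requires the population review to be blinded.

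This is separate from the other exclusion in SAP 2.3.2, that of Treatment patients whose procedure stopped before any implant was tried. Both readings of the ITT paragraph exclude those patients, and that is a departure from protocol 6.2 in its own right.

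**Working it through.** **1. Follow one patient through the rules.** Take a patient randomized to Control who is later found to have missed an inclusion criterion.

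| Rule | In the ITT set? |
|---|---|
| SAP 2.3.2, first ITT sentence | No |
| SAP 2.3.2, screen failure bullet | No, listed only |
| SAP 2.3.2, next ITT sentence | Yes |
| SAP 2.3.3 | Yes; may leave per-protocol |
| SAP 2.4.1.2 | Yes; counted there as a deviation |
| Protocol 6.2 | Yes, as Control |

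A Treatment patient with an implant attempt gets the same six answers.

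**2. Test the strict reading against the nesting of the sets.** SAP 2.3.2 draws per-protocol from as-treated, and as-treated from ITT. If ineligible patients were already outside ITT, the eligibility item in SAP 2.3.3 would have nobody to remove, and the eligibility row of the deviation table in SAP 2.4.1.2 would always be empty. The strict reading makes both redundant. The lenient reading makes the eligibility clause in the first ITT sentence redundant. Neither reading gives effect to all the text.

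**3. Reproduce the plan's sample size.** Inputs from protocol 6.6 and SAP 2.2: difference −2.4 − (−12.4) = 10 ml, SD 13 ml in both groups, two-sided alpha 0.05, 3:1 allocation, Student's t-test. Power comes from the noncentral t distribution with nT + nC − 2 degrees of freedom and noncentrality 10 / (13 × √(1/nT + 1/nC)).

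- 54 + 18 = 72: power 79.6%.
- 57 + 19 = 76: noncentrality 10 / (13 × √(4/57)) = 2.90, power 81.8%.

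So 76 is the smallest 3:1 total that reaches 80%, as the plan states.

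**4. Evaluable patients after the planned attrition.** 120 × (1 − 0.30) = 84, or 63 + 21. Noncentrality is 10 / (13 × √(4/63)) = 3.05 and power is 85.5%.

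**5. Illustrate an eligibility exclusion on top of that.** The share removed is assumed, because the documents give none. It is taken as equal in both arms and independent of attrition.

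| Assumed share removed | Evaluable (Treatment + Control) | Power |
|---|---|---|
| 0% | 63 + 21 | 85.5% |
| 2% | 61.7 + 20.6 | 84.8% |
| 5% | 59.9 + 20.0 | 83.6% |
| 10% | 56.7 + 18.9 | 81.5% |
| 15% | 53.6 + 17.9 | 79.3% |

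One Control patient is 1/21 = 4.8% of the evaluable Control arm, so a few discretionary decisions could move the Control mean even where power hardly changes.

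**The case against.** The best defence is that the eligibility clause only describes the gate before randomization. Protocol 3.5.3.4 randomizes a subject once all criteria are judged met, so everyone randomized has passed, and the next ITT sentence follows naturally with its "therefore" wording. The follow-up categories in protocol 3.7.2 fit this view: two kinds of screen failure arise before randomization, one arises in the Treatment arm before an implant attempt, and none takes in a randomized Control. SAP 2.3.2 also refers to a Fig 1 that is missing from the text available, and it may show the intended flow.

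Much of this stands. A reader might infer from the first ITT sentence that an ineligible randomized patient is simply dropped from the primary analysis. The documents do not support that: the next sentence, SAP 2.3.3, SAP 2.4.1.2 and protocol 6.2 all point to keeping the patient. But the defence does not remove the conflict. SAP 2.3.3 expects some patients to have an unmet criterion, so passing the gate and meeting every criterion are not the same thing in this plan. The next sentence also presents itself as a consequence of the definition, not as a correction to it.

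A second tempting inference is that core-laboratory re-reading will be used to remove patients. MR grade, LVEF and LVEDD are entry criteria. Under protocol 4.2.2.1 the core laboratory analyzes all baseline and follow-up echocardiograms, and "Echocardiographic analysis will be done in batches" that mix subjects and visits. SAP 2.3.1 takes echocardiographic data from the core-laboratory databases. This shows how a discrepancy could come to light, but no text says that these readings re-decide eligibility. The batching is described as serving consistency and blinding, and the echocardiogram protocol in Appendix E is not reproduced. The route is an inference only.

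**Conclusion.** The concern holds as an internal contradiction about the primary analysis set. Two statements in SAP 2.3.2, read literally, exclude randomized patients of either arm who missed a criterion. One further statement in the same section, two elsewhere in the SAP and protocol 6.2 keep them. How such a patient is handled is therefore undecided when the sponsor approves populations, which puts intent-to-treat at risk.

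A reader might also infer that the trial would be underpowered. That is not shown. Power stays above 80% at an assumed 10% loss and falls just below it at 15%, and every such share is an assumption. The number of patients affected cannot be estimated from the documents and may be zero.

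Two limits apply. The missing Fig 1 could settle what was intended, although the text would still need to agree with it. The protocol compared here is revision AD, while SAP section 1 says it elaborates revision AA; the contradiction inside the SAP does not depend on which revision is used.

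**What to change.** Amend SAP 2.3.2 before populations are assigned:

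1. In the first ITT sentence, delete the clause that requires eligibility criteria to be fulfilled.
2. In the screen failure bullet, confine the eligibility part to patients who consented but were not randomized because a criterion was unmet.
3. Add that a randomized patient with an eligibility violation stays in the ITT set in the randomized arm, and that exclusion is possible only from the per-protocol set, under the case-by-case review in SAP 2.3.3. That section says such patients may be excluded, so the addition should not make removal automatic.
4. Check that Fig 1 agrees.

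Leave the second part of the screen failure bullet in place for now. It covers Treatment patients stopped before an implant attempt. Confining the whole bullet to non-randomized patients would leave them in no set except the enrolled population. Their absence from ITT conflicts with protocol 6.2 and should be resolved as its own point, with a set named for them.

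The cost is SAP wording. No new data are needed and the minimum of 76 evaluable patients does not change.

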3.7.1.2 Treatment Group

For subjects randomized to the Treatment group, the CARILLON Mitral Contour System procedure will be performed. The implant procedure is described in Appendix A: Instructions For Use.

Pre-medication will be according to institutional procedures for cardiac catheterization. Additionally, subjects will be heparinized prior to the angiographic procedure according to institutional policies. Anti-platelet therapy is not required in the REDUCE FMR Trial, however, individual Investigators may prescribe such medications in accordance with their institution's standard of care or as necessary to treat other concurrent cardiac conditions. The use of anti-platelet therapy will be noted on the case report forms.

Either Transesophageal Echocardiogram (TEE) or Transthoracic Echocardiogram (TTE) may be used during the implant procedure to evaluate the safety and effectiveness of device placement. If TEE is used during the index procedure, the assessment of the left atrial appendage clot exclusion criteria (required for subjects with existing atrial

fibrillation) may be made immediately prior to randomization and the index procedure (i.e., a separate TEE is not required.)

All subjects randomized to the Treatment group will have coronary angiography performed prior to the CARILLON implant attempt. This is in order to establish the baseline flow characteristics of the coronary arterial vessels in the same location (AV groove) as the coronary sinus/great cardiac vein. If coronary artery flow compromise is noted during the CARILLON implant procedure, the CARILLON device can be recaptured. At the investigator and proctor's discretion, another CARILLON device attempt can occur if the device can be placed in a portion of the coronary sinus/great cardiac vein where coronary flow is not compromised.

However, if there is **clinically significant** coronary artery compromise, mitral stenosis, systolic anterior motion or other safety issues, the CARILLON implant will be recaptured and the procedure ended.

If the patient becomes hemodynamically unstable and/or no CARILLON device implant is attempted, the subject will be classified as a Procedural Screen Failure in the Treatment group and will be followed through 1-month with a safety assessment only (full 1-month follow-up assessments are not necessary), then exited from the study.

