6.3.2.1 Safety

The following secondary safety endpoints will measure the effect of the CARILLON Mitral Contour System on clinical safety parameters of interest, relative to the Control population

- To document the difference in the rate of major adverse events between randomized groups, at 1 and 12-months post randomization.

Major Adverse Events are defined as a composite of the following:

- Death
 - Myocardial Infarction
 - Device Embolization
 - Vessel Erosion, requiring percutaneous or surgical intervention
 - Cardiac Perforation, requiring percutaneous or surgical intervention
 - Occurrence of cardiac surgery or percutaneous coronary intervention associated with device failure
- To assess the rate of heart failure hospitalizations (number of admissions, and total associated days in the hospital), from the time of the index procedure through twelve months of follow-up

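### The SAP's ITT set drops randomized Treatment patients whose procedure stopped before an implant attempt, so they enter no between-group safety comparison

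*SAP*

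**What the plan says.** SAP 2.3.2 describes the ITT set as follows: "This population will therefore include all randomized patients except the patients for whom the procedure was discontinued before an implant attempt". The patients left out go to the screen failure population, which takes in "all enrolled patients who did not meet all eligibility criteria or randomized to treatment group but procedure discontinued before an implant attempt" and for which only a listing is planned. The As-Treated (AT) set is a subset of ITT, and the Per Protocol (PP) set is a subset of AT. Secondary endpoints (SAP 2.4.3) run on ITT, then AT and PP. Adverse events (2.4.4) and mortality and SAEs (2.4.5) run on ITT.

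Protocol 6.2 analyses all subjects by randomized group and adds that "subjects randomized to the Treatment group but who do not receive a permanent implant will be included". The MAE endpoint in Protocol 6.3.2.1, repeated in 3.2.2.1, is "To document the difference in the rate of major adverse events between randomized groups, at 1 and 12-months post randomization".

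Protocol 3.7.1.2 and 3.7.2 call patients stopped before an attempt Procedural Screen Failures and place them in the randomized Treatment group. Under 3.7.3.1 they are observed overnight, have the discharge evaluations and a 1-month safety assessment, and then exit.

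**The concern.** This is a post-randomization exclusion that can act in one arm only: no Control patient has an attempt to be stopped before, and all Controls stay in the set. It may also be related to outcome. Protocol 3.7.1.2 reads "If the patient becomes hemodynamically unstable and/or no CARILLON device implant is attempted, the subject will be classified as a Procedural Screen Failure", so instability during the procedure is part of how the category is described. A set conditioned in this way should not carry the ITT label, and the 1-month safety comparison would omit patients whose data are in hand.

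Three wording problems make membership less clear still:

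- The ITT sentence covers "all patients who fulfill all eligibility criteria and either underwent the procedure and on whom a device implant was attempted" or Control patients. On its face the eligibility condition could remove a randomized patient of either arm. The SAP's following sentence names no-attempt as the only exception, and SAP 2.3.3 treats eligibility failures as a PP matter.
- The AT explanation, "This population will therefore include all randomized patients except the patients who underwent the procedure but were not implanted", read alone, leaves the no-attempt patients' status unclear. The AT definition itself keeps them out.
- Protocol 3.7.1.2 refers to instability and/or no attempt, while 3.7.2 refers only to discontinuation before an attempt.

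**Working it through.** **Set membership.** For a Treatment patient stopped before an attempt:

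- ITT: out, by the stated exception.
- AT: out, because it is drawn from ITT and requires the randomized therapy to have been given.
- PP: out, because it is drawn from AT.

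Such a patient is in 0 of the 3 sets used for comparisons. Under Protocol 6.2 the patient would be in the Treatment group.

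**The plan's own figure.** Protocol 6.6 gives a difference of 10 ml, SD 13 ml, two-sided alpha 0.05, 80% power and 3:1 allocation. Exact t-test power uses the noncentral t with noncentrality 10 / [13 × √(1/57 + 1/19)] = 2.90 on 74 df, which gives 81.8% for 57 + 19 = 76. With 54 + 18 = 72 it is 79.6%. So 76 is reproduced, and this point does not change it.

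**Complete-case primary analysis.** These patients exit at 1 month without a 12-month echo, and SAP 2.1.1 omits subjects without 12-month data. Change in the estimate: 0 ml.

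**1-month MAE rate (illustrative).** Treatment N = 120 × 0.75 = 90. Assume k = 3 excluded, leaving 87.

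| Events in all 90 | All randomized | SAP set, one event among the 3 | SAP set, none among the 3 |
|---|---|---|---|
| 2 | 2/90 = 2.2% | 1/87 = 1.1% | 2/87 = 2.3% |
| 12 | 12/90 = 13.3% | 11/87 = 12.6% | 12/87 = 13.8% |

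Varying k instead: with 2 events among those retained and k = 2, 5, 9 or 14, the SAP rate is 2/88, 2/85, 2/81 or 2/76, that is 2.3% to 2.6%. Over all 90 it is 2.2%, 3.3% or 4.4% if 0, 1 or 2 of the excluded patients had an event.

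**Chance that any of 3 excluded patients had an MAE.** Protocol 1.3.6 quotes 30-day rates of 1.9%, 2.8% and 13% from the earlier device studies. Applying 1 − (1 − p)³:

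- p = 1.9%: 5.6%
- p = 2.8%: 8.2%
- p = 13%: 34.1%

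These are high for patients with no attempt. By the definitions in Protocol 9.2, embolization, erosion and surgery or PCI for implant failure need an implant, so only death, MI and perforation can count.

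**LOCF sensitivity analysis.** Protocol 6.2 speaks of "imputing the last value observed (last value carried forward) for all missing endpoint evaluations". Neither document limits this to post-baseline values, and a baseline TTE is required (Protocol 3.5.1). The discharge TTE only rules out effusion. If baseline is carried forward, the change is 0 ml. With everyone else at the planning means (−12.4 and −2.4 ml), the Treatment mean is −12.4 × (90 − k)/90:

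- k = 1: −12.26, difference 9.86 ml
- k = 3: −11.99, difference 9.59 ml
- k = 5: −11.71, difference 9.31 ml

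**The case against.** The strongest reply is that the SAP follows a category the protocol created. Protocol 6.2 opens by speaking of the primary analyses. Protocol 6.6 identifies the un-implanted patients retained in the intent-to-treat analysis as Non-Implanted, a category that requires an attempt. The protocol itself labels no-attempt patients screen failures and exits them at 1 month. The phrase about randomized groups in the MAE endpoint names the arms without expressly fixing the denominator. This does not carry: 6.2 goes on to cover all subjects by randomized assignment without an attempt condition, and 3.7.1.2 puts these patients in the Treatment group.

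Several limits do stand:

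- The loss is mainly in safety events up to about 1 month. The secondary efficacy endpoints are changes to 12 months and would be missing for these patients under any ITT definition, LOCF aside.
- The number is probably small. The Synopsis and Protocol 3.4.2, 3.5.3.3 and 3.7.1.3 put venography before randomization. Protocol 1.1 describes a venous angiogram after it, so the text sets no firm bound.
- The 13% rate comes from the earliest device study; the study of the modified XE2 reports 2.8%.
- The LOCF figures isolate one effect. With about 30% attrition allowed for, the real analysis would carry values forward for many others in both arms.
- The population figures in Protocol 6.1 and SAP 2.3.2 are not shown, and the SAP cites protocol Revision AA while the protocol at hand is Revision AD.

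**Conclusion.** The concern holds and should be fixed. As written, the SAP's ITT set is a modified ITT with a Treatment-only exclusion, contrary to Protocol 6.2, and no other comparison set restores the patients. Reading the definitions is enough to establish this; it depends on no modelling.

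The practical size is probably modest but unknown, and so is the direction: the Treatment safety rate could be understated or overstated, and every size shown rests on an assumed number of patients and events. The primary complete-case result is not threatened, and Protocol 6.8 calls the secondary and observational results descriptive and supportive. The patients also remain visible in the listing, in CEC and DSMB review and in the disposition counts (SAP 2.4.1.1), but none of these is a between-group comparison.

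**What to change.** In SAP 2.3.2:

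- Define ITT as all randomized subjects by assigned group, with no eligibility or attempt condition, and use it for the primary, secondary, safety and observational analyses.
- Limit the screen failure population to patients who were not randomized.
- Keep the present set as a labelled modified-ITT sensitivity analysis.
- Align the AT explanatory sentence with the AT definition.

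Elsewhere:

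- Report 1-month MAE on all randomized patients.
- For 12-month event endpoints, censor 1-month exits at exit and state that this censoring may be informative. The Chi² and Fisher tests in SAP 2.1.3 cannot censor, so add a Kaplan-Meier estimate. It does not cover admission counts or hospital days; the SAP should say how shortened follow-up is handled for those.
- State whether LOCF carries baseline forward for these patients.
- Reconcile the descriptions of a Procedural Screen Failure in Protocol 3.7.1.2 and 3.7.2.

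The cost is SAP wording, one additional modified-ITT analysis and a Kaplan-Meier estimate, with no new data. Treatment safety rates may move slightly either way, the LOCF difference would shrink slightly if baseline is carried forward, and the Treatment arm gains a few patients with only 1 month of follow-up.
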